2.9.1.1 Adverse events of special interest / grouping of AEs

Selected tables will be produced for Adverse Events of Special Interest (AESI) (i.e., risks) defined in the latest version of case retrieval sheet (eCRS) at the time of analysis implementation (i.e., study database lock). Specifically, incidence of TEAEs that fulfill the risk search terms as defined in eCRS will be summarized by risk name and level.

2.9.1.1.1 Injection reaction related AEs

Incidence of injection site reaction AEs and injection systemic reaction AEs as collected in the relevant CRF pages will be reported as part of the AE summary tables as two preferred terms respectively. For summaries of injection systemic reaction AEs specified in this section, reaction/symptom start date and time will be compared with the injection date and time. Only reactions/symptoms within 24 hours after injections will be included (i.e., time to onset of reaction <= 24 hours). The time to onset of reaction will be derived as (reaction start date/time – injection date/time) and rounded to the closest integer in hours.

Symptoms listed in the injection site reaction or injection systemic reaction CRF pages will be summarized by providing the number and percentage of subjects with each of the symptoms and pre-specified grouping of symptoms as well as overall. These summaries will be provided for each injection up to injection 9 and cumulatively for injections after injection 9 (i.e., injections 10 to last injection) as well as cumulatively for all injections. The proportion of subjects with injection site reactions and the proportion of subjects with injection systemic reactions will be plotted against the injection sequence numbers (injections 1, 2, 3, 4, 5, 6, 7, 8, 9 and 10+).

For the injection site reaction, no grouping of symptoms will be specified. For the injection systemic reaction, symptoms will be grouped under 6 categories as defined below and the number and percentage of subjects with at least one symptom reported under the category will be provided for each category.

- Skin/mucosal tissue symptoms: Rash, Urticaria, Pruritus general, Flushing
- Respiratory compromise: Dyspnea, Bronchospasm, Chest discomfort, Cough
- Related to change in vital signs: Hypotension, Hypertension, Dizziness, Tachycardia
- Gastrointestinal symptoms: Nausea, Vomiting, Abdominal pain, Diarrhea
- Musculoskeletal/connective tissue symptoms: Arthralgia, Myalgia, Back pain
- Other manifestations: Fever, Headache, Chills, Asthenia, Fatigue, and Other

For both injection site and systemic reaction, symptoms will be summarized by injection and injection related premedication category. Details about injection related premedication category are given in Section 2.4.2.3. Injection systemic reaction will be summarized by none, any premedication and all combinations of three types of premedication. A listing of injection related reactions by injection of first occurrence, subjects and event start date will be provided.

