4.2 Rationale for dose/regimen and duration of treatment

Ofatumumab dose

The dose regimen for ofatumumab for this study is a *loading dose regimen* of 20 mg at Day 1, Day 7 and Day 14, followed by a monthly *maintenance dose regimen* of 20 mg administered every 4 weeks, starting at week 4.

This dose regimen is consistent with the dose and regimen in the Phase 3 development program of ofatumumab in RMS.

Duration of treatment

Treatment duration within the study will be 96 weeks with the primary endpoint being at 96 weeks.

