6.1.4 Treatment duration

The planned duration of treatment is 96 weeks. Subjects may be discontinued from treatment earlier as per criteria in Section 9.1.1.

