6.7.2 Instruction for prescribing and taking study treatment

The study drug (ofatumumab injections) will be administered starting at Visit 1. Drug will then be dispensed at scheduled visits throughout the treatment period. Starting at week 4, the subcutaneous injections should be administered at 4-week intervals (+/- 3 days).

Site personnel will provide training to subjects on the correct procedure for self-administration of s.c. injections. At Visit 1, subjects will receive the s.c. injection at site, where tolerability and vital signs will be assessed. Should the subject experience any tolerability event or post dose vital signs are not within reasonable limits, subject may remain at site until symptoms resolve or vital signs are within reasonable limits of baseline values.

In certain countries, e.g. Czech Republic, the local health authority requires subjects to remain at the site under observation for approximately 1 hour following first study drug dosing at Visit 1, where post vital signs will be collected. A longer observational period may be required if per investigator judgement these vital signs are not within reasonable limits of subject's baseline values. Subject or caregiver will inject the study medication under supervision of the study staff.

Following Visit 1, subjects may inject the study medication at home by themselves or have a caregiver who has been trained by the study staff on the proper technique and safety precautions, inject the study medication. Ability to self-administer injections must be demonstrated and documented before home-administration is permitted. Injection 2 (Day 7) will be overseen remotely by the designated site personnel to support the self/home administration and provide additional training as needed. Subjects will return to the site for the week 2 and 4 administrations. If a subject is unable/unwilling to self-administer injections, home-administration may be performed by another individual (e.g. partner, relative or a healthcare professional) who has accompanied the subject to the site and has been trained on and demonstrated ability to correctly administer the s.c. injections. In the exceptional circumstances, the subject may receive injections at the site, for example, subjects with severe neurological deficits should not self-administer injections.

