- ¹⁸ If the scheduled visit coincides with the day that study drug administration is scheduled, the subject should be instructed not to administer the injection before coming to the site so that the assessments can be completed prior to study drug administration.
- ¹⁹ Additional NfL and CCI sample to be collected in case of any unscheduled visit due to suspected MS relapse

CCI CCI, CCI

- ²⁰ Assessment must be completed to allow adequate time for results to be obtained before first study drug administration to ensure subject's eligibility
- Women of childbearing potential only Serum pregnancy tests will be conducted on an annual basis at site. Monthly urine pregnancy tests will be conducted between scheduled visits at home and on scheduled visits (in the absence of an annual serum pregnancy test) at site prior to the administration of study drug. The subject must contact the Investigator immediately in the case of a positive test for confirmatory testing at the Investigator's discretion.
- ²² Subject's contraception status must be reviewed and documented to ensure method of contraception continues to be appropriate per protocol requirement for highly effective contraception.
- ²³ Including corticosteroids used to treat MS relapse; any new started MS treatment as applicable (for subjects who have discontinued study medications).
- ²⁴ Visit can be performed at the site or at subject's home with support of home nursing service. In this case an additional home nursing ICF must be signed.
- ²⁵ CCI and CCI should be given to the patient minimum 7 days prior to planned first study drug dose.
- To be assessed locally. If local testing is not feasible at a site, then these tests may be done by the Central Laboratory to assess patient's eligibility.
- ²⁷ MS relapses occurring after ICF signature should be assessed according to Section 8.3.1 and recorded on the Summary of MS Relapses eCRF.
- ²⁸ One additional medication kit can be dispensed at Visit 12/week 84, and taken by the subject prior to or no later than the day of the EOS visit, to ensure the subject does not have an interruption in treatment between study completion and start of commercial ofatumumab via prescription or via PTA mechanisms.

¹³ To be completed prior to first study drug administration

¹⁴ Patient Reported Outcomes: CCI

Table 8-2 Assessment Schedule, Safety Follow-up

Period		Po	st-Treatment Follow-up				

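### The injection-reaction figure puts a cumulative 10+ proportion on the same axis as single-injection proportions, so it can show a late rise that is not there or mask a late fall

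*SAP*

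**What the plan says.** SAP 2.9.1.1.1 first sets out the tables: symptoms of site and systemic reactions are summarised "for each injection up to injection 9 and cumulatively for injections after injection 9 (i.e., injections 10 to last injection"), and also over all injections together. The next sentence defines the figure. What is plotted is "The proportion of subjects with injection site reactions and the proportion of subjects with injection systemic reactions". As to the horizontal axis, both measures "will be plotted against the injection sequence numbers (injections 1, 2, 3, 4, 5, 6, 7, 8, 9 and 10", the final category carrying a plus sign. The section gives no separate definition or denominator for the 10+ point, no rate per injection given and no adjustment for the number of injections received.

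The number of injections pooled follows from the protocol:

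- Section 4.2 gives "20 mg at Day 1, Day 7 and Day 14, followed by a monthly" dose for maintenance.
- Section 6.7.2 adds: "Starting at week 4, the subcutaneous injections should be administered at 4-week intervals (+/- 3 days").
- Section 6.1.4: "The planned duration of treatment is 96 weeks".
- Footnote 28 to Table 8-1, on the run-up to the end-of-study visit: "One additional medication kit can be dispensed at Visit 12/week 84, and taken by the subject prior to or no later than the day of" that visit.

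Injection-related reactions are named in the first secondary endpoint (Protocol Table 2-1, SAP 2.8).

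**The concern.** For injections 1 to 9 each plotted value answers the question: what share of subjects reacted to this injection? For 10+ it answers: what share reacted at least once to any injection from the tenth on? The second grows with the number of injections pooled and with how long subjects stay on treatment. The first does not. On one sequence axis the eye joins the points and reads the last as a continuation of the series.

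At stake is how the time course of a named safety outcome is read. Protocol 4.5 describes systemic reactions in the Phase 3 studies as largely confined to the first injection, and a reader will want to see whether that holds here. The study has one arm, so there is no control curve in which the same artefact would show itself.

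**Working it through.** The plan states neither a total number of injections nor a per-injection risk, so there is no figure of its own to reproduce. The injection count comes from the schedule. The risk p and the within-subject correlation ρ are assumptions, shown as ranges.

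**Injection count.** Loading: Days 1, 7 and 14 = 3. Maintenance: Weeks 4, 8, …, 92 = 23. Total 3 + 23 = 26. Injection 4 is at Week 4, so injection 9 is at Week 24 and injection 10 at Week 28. The 10+ category pools 26 − 9 = 17 injections. With the optional kit the total is 27 and the category pools 18.

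**Constant risk, independence within subjects.** P(at least one reaction in k injections) = 1 − (1 − p)^k.

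| p per injection | k = 17 | k = 18 |
|---|---|---|
| 0.1% | 1.7% | 1.8% |
| 0.5% | 8.2% | 8.6% |
| 1% | 15.7% | 16.5% |
| 2% | 29.1% | 30.5% |

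For p between 0.5% and 2% and k = 17, the 10+ point is 14.5 to 16.3 times the neighbouring single-injection points.

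**Constant risk, reactions clustered within subjects.** Let each subject's risk follow a beta distribution with mean p and correlation ρ, so a = p(1 − ρ)/ρ and b = (1 − p)(1 − ρ)/ρ. Then P(at least one) = 1 − Γ(b + k)Γ(a + b) / [Γ(b)Γ(a + b + k)]. With p = 1% and k = 17:

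| ρ | 10+ point |
|---|---|
| 0 | 15.7% |
| 0.1 | 9.4% |
| 0.3 | 5.3% |
| 0.5 | 3.4% |
| 0.8 | 1.8% |
| 1 | 1.0% |

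The false rise shrinks as reactions concentrate in the same people. It disappears only at ρ = 1.

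**Masking a fall.** Suppose risk is 1% at injection 9 and 0.1% from injection 10 on. The 10+ point is 1.7% under independence and about 1.0% at ρ = 0.1. A tenfold fall would look like a small rise or a plateau.

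**Dependence on retention.** At p = 1% and independence, a subject who receives only 8 of the 17 late injections has probability 1 − 0.99^8 = 7.7% of counting, not 15.7%. Missed doses and early stopping therefore pull the point down, for reasons unrelated to risk per injection.

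**Scale, and the per-injection alternative.** Take 555 subjects, no dropout, p = 1% and independence. About 555 × 0.01 = 5.6 subjects count at each single injection and 555 × 0.157 = 87 at 10+. As a rate, 555 × 17 × 0.01 = 94.35 expected reactions over 555 × 17 = 9,435 injections is 1.0%, the same as the neighbouring points. That expected rate is p whatever the value of ρ.

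**The case against.** Several points on the other side have force.

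- **Size.** A reader might infer that the figure is bound to show a large late rise, some 15 to 16 times the preceding points. The documents do not support that. It needs a flat risk and independence between injections in the same subject. Repeat reactions in the same people are plausible, and the documents give no correlation.
- **Systemic reactions are probably not flat.** Protocol 4.5 reports them in 20.6% of ofatumumab patients in Phase 3 and describes them as limited to the first injection. If late risk were 0.1%, the 10+ point would be about 1.7%, and a first-injection peak of that order would still stand out. This background does not cover site reactions, so the concern is stronger there.
- **The pooling is partly disclosed.** The SAP describes the tabulated late category as cumulative and the axis category is 10+. That tells the reader injections are pooled, but it does not make the points comparable, and no cumulative label is required on the figure itself.
- **Alignment with the pivotal trials.** The SAP document history for amendment 2 records keeping the same injection-reaction analyses as ASCLEPIOS, and SAP 2.4.2.3 uses the same grouping for premedication. This is a good reason to keep the cumulative value somewhere. Whether the ASCLEPIOS figure used these categories cannot be checked from these documents.
- **Other outputs.** Tables for injections 1 to 9 and for the pooled categories, and a listing by injection of first occurrence, are also planned. None is specified to give a late per-injection rate.

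A reader might also infer that the secondary endpoint is distorted. It is not: the endpoint is the overall proportion of subjects with events, which this figure does not alter. The figure is descriptive, with no test attached.

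**Conclusion.** The point holds as a matter of presentation. Nine single-injection proportions share an axis with one proportion accumulated over 17 scheduled injections (18 with the optional kit), and no other planned output supplies a late rate on the single-injection scale. This takes the plotted 10+ value to be the cumulative one defined in the sentence before it; the SAP gives no other definition.

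Under a constant risk with full follow-up, the 10+ point is biased upwards relative to its neighbours unless exactly the same subjects react each time. The amount is uncertain: at an assumed 1% risk it runs from no excess (ρ = 1) to almost 16-fold (independence), and it is lower with missed doses and discontinuation. So the figure can mislead, in either direction. The documents do not establish that it will, or by how much. The point is a cheap improvement to a safety display.

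**What to change.** Amend the plotting sentence in SAP 2.9.1.1.1. For injections 10 to last, plot the number of injections with a reaction divided by the number of injections given. Alternatively, plot later injections singly, with the subjects who received that injection as denominator. State the same denominator for injections 1 to 9.

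Keep the cumulative 10-to-last proportion in the table. If it is also wanted in the figure for comparison with ASCLEPIOS, set it apart from the series and label it as any of injections 10 to last.

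The cost is a sentence or two in the SAP and a small programming change, with no new data. The one drawback is a figure that may differ slightly from the earlier programme's display; retaining the cumulative value preserves that comparison.

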2.9.1.1.2 Clinical Trial Safety Disclosure (CTSD) reports

For the legal requirements of ClinicalTrials.gov and EudraCT, two required tables on nonserious treatment emergent adverse events with an incidence greater than 5% and on treatment emergent serious adverse events and SAE suspected to be related to study treatment will be provided by system organ class and preferred term on the safety set population.

If for a same subject, several consecutive AEs (irrespective of study treatment causality, seriousness and severity) occurred with the same SOC and PT:

• a single occurrence will be counted if there is ≤ 1 day gap between the end date of the preceding AE and the start date of the consecutive AE

• more than one occurrence will be counted if there is > 1 day gap between the end date of the preceding AE and the start date of the consecutive AE

For occurrence, the presence of at least one SAE / SAE suspected to be related to study treatment / non SAE has to be checked in a block e.g., among AE's in a \leq 1 day gap block, if at least one SAE is occurring, then one occurrence is calculated for that SAE.

The number of deaths resulting from SAEs suspected to be related to study treatment and SAEs irrespective of study treatment relationship will be provided by SOC and PT. Relapse as SAE will be listed separately with timing, last previous DMT and washout period. All serious adverse events (SAE), regardless of the safety cut-off, will be summarized.

2.9.1.1.3 Infection

Infection adverse event will be summarized by:

- COVID-19 related infection vs. non COVID-19 related infection
- COVID-19 related serious infection vs. non COVID-19 related serious infection
- Within COVID-19 related infection: serious infection vs. non serious infection
- COVID-19 related infection by CTCAE grade
- Non COVID-19 related infection by CTCAE grade
- Serious COVID-19 related infection by CTCAE grade
- Non serious COVID-19 related infection by CTCAE grade

Number of subjects with at least one infection AE will also be provided. AEs related to malignancies will also be summarized.

2.9.2 Deaths

Death, if meaningful number of cases reported (i.e., 5 or more cases), will be summarized by providing the number and percentage of subjects, otherwise only listing will be provided. All deaths as recorded in the final database (i.e., up to database lock) will be included.

2.9.3 Laboratory data

Data summaries will be provided in SI units. The summary of laboratory evaluations will be presented for three groups of laboratory tests: Hematology, Chemistry and Urinalysis. On presenting summary statistics, laboratory data will be grouped and displayed in an alphabetical order within the Hematology and Chemistry groups.

Descriptive summary statistics (mean, median, standard deviation, Min and Max) of the change from baseline in the laboratory result to each study visit-window will be presented. Change from baseline will only be summarized for subjects with both baseline and post baseline values and will be calculated as:

change from baseline = post baseline value – baseline value

The number and percentage of subjects with new or worsening laboratory abnormalities based on CTC grade (CTCAE version 5.0) in each visit-window (grade 1/2, grade 3/4) and at any time

post baseline will be presented. Subjects with specific laboratory abnormalities based on CTC grades >=3 will be listed.

Number of subjects with newly occurring liver enzymes abnormalities will be summarized. Newly occurring liver enzymes abnormalities are defined in Section 5.3.1.

For continuous variables databased as < lower limit, these will be imputed as being half of the lower limit. For continuous variables databased as > upper limit, there will be imputed as equal to the upper limit,

All above summaries include only data up to and including safety cut off date (see Section 2.9 for safety cut off date).

2.9.3.1 Other special lab results

Other non-routine laboratory data include B-cell counts, total IgG, total IgM, and other biomarkers such as neurofilaments. All data will be listed appropriately.

The B-cell counts, total IgG, total IgM, neurofilaments, lymphocytes and neutrophils will be summarized using descriptive statistics by visit-window. IgG, IgM, lymphocytes and neutrophils will also be summarized by visit-window and last prior DMT.

In addition, number and percentage of subjects with B-cells < the lower limit of normal (LLN) or < their baseline value (i.e., B-cell depleted) will be presented by visit window. For subjects who entered the safety follow-up, number and percentage of subjects with B-cell recovery (above LLN) will be summarized by SFU visit-window.

Number and percentage of subjects with IgG and IgM below LLN and meet the notable low level criteria in IgG or IgM by visit window will be provided. IgG and IgM will also be summarized by visit window and last prior DMT. A notably low IgG level is defined as a level that is ≤ 4.5 g/L (20% below LLN) and ≤ 0.36 g/L (10% below LLN) for IgM. LLN is 5.65 g/L for IgG and 0.4 g/L for IgM. For subjects who had IgG or IgM below LLN at the time of entering SFU, number and percentage of subjects with IgG or IgM recovery (above LLN) will be summarized by SFU visit-window.

Number and percentage of subjects with lymphocytes and neutrophils below LLN and meet the notable abnormalities by visit window will be provided. Lymphocytes and neutrophils will also be summarized by visit window and last prior DMT. Notable abnormalities for lymphocytes and neutrophils are listed in Table 2-12.

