- 16. Any of the following chronic, severe conditions or treatments that may impact the compliance of the study:
 - History of, or current, significant cardiac disease including cardiac failure (NYHA functional class II-IV), myocardial infarction (within 6 months prior to screening), unstable angina (within 6 months prior to screening), transient ischemic attack (within 6 months prior to screening), stroke, cardiac arrhythmias requiring treatment or uncontrolled arterial hypertension
 - Concomitant clinically significant cardiac arrhythmias, e.g. sustained ventricular tachycardia and clinically significant second or third degree AV block without a pacemaker on screening electrocardiogram (ECG)
 - History of or active severe respiratory disease, including Chronic Obstructive Pulmonary Disease, interstitial lung disease or pulmonary fibrosis
 - Subjects with asthma requiring regular treatment with oral steroids
 - Severe hepatic impairment (Child-Pugh class C) or any chronic liver or biliary disease

- Subjects with severe renal impairment (Glomerular Filtration Rate < 30 ml/min/ 1.73 m^2
- Any medically unstable condition as determined by the Investigator
- severe hypoproteinaemia e.g. in nephrotic syndrome
- 17. Any of the following abnormal laboratory values as confirmed by the central laboratory prior to first study drug administration:
 - Lymphocyte count $<500/\text{mm}^3$ ($<0.5 \times 10^9/\text{L}$) in patients discontinuing fumarates
 - Serum IgG < 500 mg/dL (according to central laboratory range)
 - Any other clinically significant laboratory assessment as determined by the Investigator (e.g. significant anemia, neutropenia, thrombocytopenia, signs of impaired bone marrow function)
- 18. Subjects with any of the following neurologic/psychiatric disorders prior to first study drug administration:
 - Score "yes" on item 4 or item 5 of the Suicidal Ideation section of the Columbia-Suicide Severity Rating Scale (C-SSRS), if this ideation occurred in the past 6 months, or "yes" on any item of the Suicidal Behavior section, except for the "Non-Suicidal Self-Injurious Behavior" (item also included in the Suicidal Behavior section), if this behavior occurred in the past 2 years.
- 19. History of hypersensitivity to the study drug or any of the excipients or to drugs of similar chemical classes

6 **Treatment**

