2.1.1 General definitions

Below some general definitions to be used in the rest of the document are summarized.

Table 2-1 General Definitions

Table 2-1 General Deminitions	
Study treatment/Study drug	The investigational drug (ofatumumab) will be referred as study treatment or study drug.
Date of first administration of study drug/first dose date	The first dose date of active study drug administration.
Date of last administration of study drug/last dose date	The last dose date of active study drug administration.
Study Day 1 or Day 1	The date of first administration of study drug/first dose date.
Study Day	 All other study days will be labeled relative to Day 1. For events with dates on or after Day 1, study day for the event is calculated as (event start date – first dose date + 1). For events with dates before Day 1, study day for the event is calculated as (event start date – first dose date). Day 0 will not be used.
Duration of an event	Duration of an event is calculated as (event end date – event start date +1).
1 month	30 days; to be used in defining 6-month confirmed disability worsening or improvement.
4 weeks	28 days; to be used in determining target days of scheduled visits. It is based on the scheduled injection frequency for ofatumumab (during the maintenance phase).
Day post-study drug discontinuation	Day post-study drug discontinuation for a particular event is calculated as (event start date – study drug discontinuation date).
Baseline	Baseline is the last assessment obtained prior to the first administration of study drug. No visit windows will be needed for the identification of baseline assessment.
	For pulse and blood pressure vital sign values, the baseline is the average of the non-missing values of the 3 measurements taken on the last visit prior to the first administration of study drug. The pre-injection assessment values on Day 1 vital sign case report form (CRF) page will not be used for baseline derivations.

On-treatment period	On-treatment period includes days from the first injection date until 30 days after the last injection date. This definition considers subjects on ofatumumab are scheduled to inject every 28 +/- 3 days. For calculation of compliance to study drug administration, similar definition of on-treatment period will be used.

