^{*} Data collected from Day 1 protocol scheduled visit will not be mapped to the visit windows due to different data collection on this visit.

Table 2-6 Visit-windows for routine laboratory values

Visit-window	Start day	Target day	End day
Week 4	1	28	56
Week 12	57	84	126

Week 24	127	168	252
Week 48	253	336	420
Week 72	421	504	588
Week 96	589	672	762

Table 2-7 Visit-windows for B-cell counts, IgG levels, IgM levels, PROs*

Visit-window	Start day	Target day	End day
Week 4	1	28	98
Week 24	99	168	252
Week 48	253	336	420
Week 72	421	504	588
Week 96	589	672	762

^{*}Patient Reported Outcomes include CCI

Table 2-8 CCI LCVA, CCI

Visit-window	Start day	Target day	End day
CCI			504
Week 96	505	CCI	762

Table 2-9 Visit-windows for biomarker data

Visit-window	Start day	Target day	End day
Week 4	1	28	56
Week 12	57	84	126
Week 24	127	168	210
Week 36	211	252	294
Week 48	295	336	378
Week 60	379	420	462
Week 72	463	504	546
Week 84	547	588	630
Week 96	631	672	762

Table 2-10 Visit-windows for eCSSRS

Visit-window	Start day	Target day	End day
Week 2	1	14	21
Week 4	22	28	42
Week 8	43	56	70
Week 12	71	84	126
Week 24	127	168	210
Week 36	211	252	294
Week 48	295	336	378
Week 60	379	420	462
Week 72	463	504	546
Week 84	547	588	630
Week 96	631	672	762

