2.1.2.2 Visit windows after study drug discontinuation

For summaries of data collected after study drug discontinuation, data from both treatment epoch and safety follow-up epoch will be considered. Participants who prematurely discontinue the study drug will be required to have their EOS visit as soon as possible and enter into the SFU according to the assessment schedule in protocol Table 8-2. In the SFU, all assessments are relative to EOS visit. Day 1 will be the first day after EOS visit. The visit window definitions for SFU Visit 1 and Visit 2 are provided in Table 2-11. The SFU Visit 2 will be the last clinic visit and the end of SFU Visit will be performed by telephone contact. Additional SFU Visit will be required if participants have either IgG or IgM < screening or LLN, and they will be performed outside of the study.

Table 2-11 Visit-windows after study drug discontinuation

Visit-window	Start day	Target day	End day
SFU Visit 1	1	84	126
SFU Visit 2	127	168	210

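### SAP 2.9.3.1 labels any B-cell count below baseline as depletion, so a normal count can be both 'depleted' and 'recovered', and the recovery denominator includes subjects who were not below LLN

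*SAP*

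**What the plan says.** All the rules are in SAP Section 2.9.3.1 (Other special lab results).

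- Depletion, by visit window: "number and percentage of subjects with B-cells < the lower limit of normal (LLN) or < their baseline value (i.e., B-cell depleted"). The SAP sets no minimum fall from baseline.
- Recovery: "For subjects who entered the safety follow-up", the "number and percentage of subjects with B-cell recovery (above LLN) will be summarized by SFU visit-window". There is no baseline condition, and no requirement to have been low on entry.
- IgG and IgM, same section: recovery is also above LLN, but the population is restricted: "For subjects who had IgG or IgM below LLN at the time of entering SFU".

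Supporting definitions are in SAP Section 2.1. "Baseline is the last assessment obtained prior to the first administration of study drug", so for B-cells it is a single value. SAP Table 2-7 ("Visit-windows for B-cell counts, IgG levels, IgM levels, PROs") sets on-treatment windows at Weeks 4, 24, 48, 72 and 96, and Table 2-11 adds two SFU windows. For summaries after stopping drug, "data from both treatment epoch and safety follow-up epoch will be considered". Neither document gives another definition of B-cell depletion or a numeric LLN for B-cells; Section 2.9.3.1 states LLN values only for IgG and IgM.

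**The concern.** A categorical depletion table should tell the reader how many subjects reached a low B-cell count and how many did not. Once any fall below a single pre-dose value is enough, a subject whose count stays in the normal range is counted with those whose B-cells are nearly absent.

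Recovery uses a different yardstick, so the two percentages are not complements. An unchanged count can be reported as depleted at the end of treatment and as recovered at the first follow-up visit. Subjects with nothing to recover from can also enter the numerator and denominator of the recovery percentage.

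Intermediate counts, where the label goes wrong, are foreseeable. Protocol Section 6.7.2 allows dosing to resume after missed injections, SAP Section 2.4.1 tabulates missed doses up to a category above 9, and Protocol Section 16.1.4 allows interruption for low IgG. The recovery figure will also be read with Protocol Section 16.1.3 in mind, which refers to normalised B-cell counts after discontinuation when it discusses live vaccines.

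**Working it through.** The plan gives no figure to reproduce, because this is a descriptive summary with no test or sample size. The check applies the written rules literally. Neither document gives a B-cell LLN, so counts are scaled to LLN = 1. Write *b* for baseline and *c* for the later count.

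**Rules**

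- SAP depleted: *c* < 1 or *c* < *b*
- SAP recovered: *c* > 1
- LLN-only alternative: depleted if *c* < 1, recovered if *c* ≥ 1

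**Cases (multiples of LLN)**

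| *b* | *c* | SAP depleted | SAP recovered | LLN-only depleted | Comment |
|---|---|---|---|---|---|
| 3 | 0.1 | yes | no | yes | as intended |
| 3 | 2 | yes | yes | no | normal count, both labels |
| 3 | 2.9 | yes | yes | no | small fall, normal count, both labels |
| 3 | 3.2 | no | yes | no | risen above baseline |
| 0.5 | 0.8 | yes | no | yes | same label under either rule |
| 0.5 | 1.5 | no | yes | no | consistent |
| 3 | 1 | yes | no | no | exactly at LLN |
| 1 | 1 | no | no | no | exactly at LLN, neither SAP label |

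**Overlap.** Both SAP labels apply when *c* > 1 and *c* < *b*, which is every count strictly between LLN and baseline. Under the LLN-only rule the overlap is empty and every count gets exactly one label.

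**Effect on the depletion percentage.** The SAP rule is a union of two conditions, so

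SAP depleted % = % with *c* < LLN + % with LLN ≤ *c* < *b*.

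The SAP figure can therefore never be lower than the LLN-only figure. The excess is the share of subjects with a count that is not low but is below baseline.

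**Effect on the recovery percentage.** Let *a* be the share of SFU entrants who are not below LLN at entry and are above LLN at the visit summarised. Suppose the remaining 1 − *a* were below LLN at entry, and a fraction *p* of them recover. Then

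reported recovery = *a* + (1 − *a*)*p*, and the excess over *p* is *a*(1 − *p*).

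The excess is zero only if *a* = 0 or *p* = 1. Neither document gives *a* or *p*, so its size cannot be stated.

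**Where the contradiction would show.** Recovery is summarised only in SFU windows. With *b* = 3 and *c* = 2 throughout, a subject is depleted in the Week 96 window and recovered at SFU Visit 1. If the depletion table is also run on SFU windows, which the SAP does not settle, both labels apply at the same visit.

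**The case against.** The strongest reply is that little depends on this table. No B-cell endpoint is named in the readable objectives tables of either document, SAP Section 2.11 lists PD analyses as not applicable, and nothing in the relapse-rate test uses the label. Protocol Section 1.1 reports a marked fall in circulating B-cells with intravenous ofatumumab, so most on-treatment counts should be below LLN under either rule. Section 2.9.3.1 also provides listings and descriptive statistics of B-cell counts, where intermediate values can partly be seen. All of this stands and limits the size of the point. It does not make the label correct, and summary statistics do not count the subjects who failed to reach a low value.

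A second reply is that the sentence may intend two separate counts, one against LLN and one against baseline. Even then, the label 'depleted' still covers the below-baseline count. Protocol Section 9.2.1 uses a similar screening-or-LLN phrase for immunoglobulins, which suggests shared wording rather than a considered threshold. That supports clarifying the text.

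Three stronger readings are tempting, but the documents do not support them.

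- *The trial's pharmacodynamic readout is invalid.* B-cells are handled as special laboratory data within safety, as noted above.
- *About half of subjects will be wrongly called depleted.* With no drug effect and exchangeable continuous counts, the chance of falling below one's own baseline is 0.5, so the SAP rule would label at least about half depleted. That describes an inert product, and every subject here receives an anti-CD20 antibody. It shows that the definition is unspecific; it does not forecast this trial.
- *Exclusion criterion 17 lets in subjects with low B-cells because its floor applies only "in patients discontinuing fumarates".* That floor is on total lymphocytes, so it neither guarantees nor prevents a B-cell count below LLN in either group. A subject who enters below LLN and stays there is also labelled depleted under the LLN-only rule. Such subjects are a reason to show baseline status, not evidence against the 'or' clause.

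**Conclusion.** The point holds as a definitional error of modest consequence. Followed as written, SAP Section 2.9.3.1 classes normal counts as depleted, gives two opposing labels to every count between LLN and baseline, and computes recovery over subjects who need not have been low. The section's own IgG/IgM rule avoids both problems by using LLN on both sides and a restricted denominator.

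The effect is confined to one descriptive safety laboratory summary and does not reach the primary analysis. The depletion percentage can only be overstated relative to an LLN-only rule. The recovery percentage is overstated by *a*(1 − *p*) as defined above. Neither amount can be estimated from the documents. The expectation that the depletion effect is small rests on the B-cell reduction reported for intravenous dosing. The statement that an unchanged count can switch labels holds only when the later visit falls in safety follow-up. The correction should be made before the tables are produced.

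**What to change.** In SAP Section 2.9.3.1:

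1. Define B-cell depleted as a count below LLN, and recovered as a count at or above LLN.
2. Limit the recovery denominator to subjects below LLN at SFU entry, as is done for IgG and IgM.
3. Tabulate depletion by baseline status (at or above LLN; below LLN).
4. Report the number below own baseline as a separate row without the depletion label. Keeping this row is worthwhile: Section 2.9.3 describes change from baseline after naming haematology, chemistry and urinalysis, and Section 2.9.3.1 promises only descriptive statistics for B-cells.
5. State whether the depletion summary covers SFU windows.

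The cost is revised wording, one derivation change and a small addition to the table shell. No new samples or visits are needed. The depletion percentage may come out slightly lower.
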